5.2.2 Subject Exclusion Criteria

1. Subjects who do not conform to the above inclusion criteria;
2. Subjects who have a clinically relevant history or presence of gastrointestinal (especially associated with vomiting), respiratory, renal, hepatic, haematological, lymphatic, neurological (especially if associated with balance disorders or vomiting e.g. migraine or labyrinthitis), cardiovascular, psychiatric, musculoskeletal, genitourinary, immunological, dermatological, connective tissue diseases or disorders;
3. Subjects who have a clinically relevant surgical history;
4. Subjects who are currently taking any of the following classes of diabetes medications: thiazolidinediones, dipeptidyl peptidase IV inhibitors ('gliptins'), GLP-1 analogues, and insulin;
5. Subjects who have a history of relevant and severe atopy e.g. asthma, angioedema requiring emergency treatment, severe hayfever requiring regular treatment (i.e. taking antihistamines and/or glucocorticoids more regularly than 3 times a week), severe eczema requiring regular treatment (i.e. taking antihistamines and/or glucocorticoids more regularly than 3 times a week);
6. Subjects who have a history of relevant drug hypersensitivity;

CONFIDENTIAL

Synoptic Clinical Study Protocol
Version 2.0 - 05/08/2017

EudraCT Number: 2017-000380-33

7. Subjects who have a history of alcohol abuse or alcohol dependence according to DSM-IV criteria within the last 2 years;
8. Subjects who have a history of drug or substance abuse according to DSM-IV criteria within the last 2 years;
9. Subjects who have a history of clinically significant migraine as judged by the Investigator. Subjects can be included if they have not had a migraine for the last 3 years;
10. Subjects with a history of pancreatitis or pancreatic cancer;
11. Subjects who consume more than 21 units of alcohol a week (unit = 1 glass of wine (125 mL) = 1 measure of spirits = $\frac{1}{2}$ pint of beer);
12. Subjects who have a significant infection or known inflammatory process on screening;
13. Subjects who have acute gastrointestinal symptoms at the time of screening or admission (e.g. nausea, vomiting, diarrhoea, heartburn);
14. Subjects who have an acute infection such as influenza at the time of screening or admission;
15. Subjects who have used prescription drugs within 2 weeks of first dosing. For Part B, patients are allowed to be treated for their diabetes with monotherapy with a sulphonylurea, metformin, or a SGLT-2 inhibitor, dual therapy with any two of the following drug types: a sulphonylurea, metformin, and/or a SGLT-2 inhibitor; triple therapy with a sulphonylurea, metformin, and a SGLT-2 inhibitor. In addition, patients in Part B are allowed to take hypolipidaemic and/or antihypertensive treatments, provided that the doses have not been altered within the 4 weeks prior to entering the study. Other medications may be allowed if the Investigator and Sponsor both agree that they will not affect the outcome of the study or the safety of the subject.
16. Subjects who have used over the counter medication excluding routine vitamins and paracetamol but including megadose (intake of 20 to 600 times the recommended daily dose) vitamin therapy within 7 days of first dosing, unless agreed as not clinically relevant by the Principal Investigator and Sponsor;
17. Subjects who have donated blood within 3 months prior to screening;
Subjects who have donated plasma within the 7 days prior to screening;
Subjects who have donated platelets within the 6 weeks prior to screening
18. Subjects who have used any investigational drug in any clinical trial within 3 months of their first admission date;
19. Subjects who have received the last dose of investigational drug greater than 3 months ago but who are on extended follow-up;
20. Subjects who have previously received Y14;

CONFIDENTIAL

21. Subjects who are vegans, vegetarian or have any dietary restriction (unless agreed as not clinically relevant by the PI and Sponsors);
22. Subjects who cannot communicate reliably with the Investigator;
23. Subjects who are unlikely to co-operate with the requirements of the study;
24. History or evidence of abnormal eating behaviour, as observed through the Dutch Eating Behaviour (DEBQ) and SCOFF questionnaires [24,25] at screening.

5.2.3 Restrictions

In Part A (SAD) subjects will be admitted to the clinical unit on Day -1 and will remain in the clinical unit under supervision until discharge on Day 4 (at least 72 h postdose) or when C_{max} is achieved, whichever is later. Subjects will be required to attend outpatient visits as described

In Part B (MAD) subjects will be admitted to the clinical unit for 6 inpatient stays: Day -2 (admission) to Day 4 (discharge), Day 8 (admission) to Day 9 (discharge), Day 15 (admission) to Day 16 (discharge), Day 22 (admission) to Day 23 (discharge), Day 29 (admission) to Day 31 (discharge), and Day 36 (admission) to 37 (discharge). Subjects will return to the clinical unit for outpatient visits as described in Table 17.2.

For both Part A and Part B, the inpatient stays and outpatient visits may be amended upon review of safety, tolerability and PK data from previous cohorts or study part.

Subjects will receive a standard diet whilst resident in the clinical unit and will only consume foodstuffs provided by the clinical unit. Subject's energy intake at each meal, along with fluid intake and output will be recorded during the inpatient stays. For Part B, study participants will be provided with a dietary advice sheet providing information with regards to a healthy eating diet which they are recommended to follow when they have been discharged from the clinical unit.

For Part A and Part B subjects should refrain from the following:

- Subjects should refrain from strenuous exercise for 48 h before screening, prior to each admission, throughout each inpatient stay and for 48 h prior to each outpatient visit.
- Subjects should refrain from alcohol and/or xanthine containing products (e.g. caffeine) for 48 h prior to screening and admission, during the inpatient stay, and for 48 h prior to each outpatient visit.
- Subjects should refrain from smoking for the duration of the study (until after the final follow-up visit).
- Subjects should refrain from eating foodstuffs that contain poppy seeds for 7 days prior to screening and 7 days prior to each admission, as these may result in a positive urine test for opiate consumption.
- Subjects should refrain from taking medications during the study as described in Section 6.5.

CONFIDENTIAL

Synoptic Clinical Study Protocol
Version 2.0 - 05/08/2017

EudraCT Number: 2017-000380-33

5.2.3.1 Avoidance of Pregnancy**Instructions for Male Subjects**

There is no information about effects that Y14 could have on the development of the foetus in humans. Therefore, it is important that the partners of male subjects do not become pregnant during the study and for a total period of 3 months after the male subject has taken the last dose of Y14.

As a precaution, all male subjects should avoid fathering a child by either true abstinence or the use of 2 effective means of contraception (see Section 5.2.3.2).

As there is no information about Y14 being secreted in the ejaculate, male subjects (including men who have had vasectomies) whose partners are currently pregnant should use barrier methods for the duration of the study and for a suitable time afterwards (e.g. 1 month). This is to ensure that the foetus is not exposed to the investigational medicinal product (IMP) in the ejaculate.

5.2.3.2 Acceptable Forms of Contraception

Highly effective methods of birth control are defined as those which result in a low failure rate (i.e. less than 1% per year) when used consistently and correctly.

These include male vasectomy with confirmation of surgical success, female sterilisation (i.e. documented bilateral tubal ligation), hormonal methods of contraception (oral, implanted or transdermal) or an intrauterine device (IUD).

Where there is a possibility of pregnancy one of the above highly effective methods should be used in combination with male condoms.

True abstinence is acceptable when this is in line with the preferred and usual lifestyle of the subject. Periodic abstinence (e.g., calendar, ovulation, symptothermal, post-ovulation methods) and withdrawal are not acceptable methods of contraception.

5.2.3.3 Time Period for the Collection of Pregnancy Information

All pregnancies in female partners of male subjects receiving at least one dose of IMP will be recorded from first dose to 3 months after the final dose.

5.2.3.4 Follow-up in the Event of a Pregnancy

If the female partner of a male subject, who has received Y14 becomes pregnant the pregnancy will be recorded. The ethics committee and the Sponsor will be informed. The subject will be asked to provide information on the outcome of the pregnancy, including premature termination should the case arise.

Spontaneous miscarriage and congenital abnormalities will be reported as SAEs.

The follow-up period will be deemed to have ended when the health status of the child has been determined on its birth.

CONFIDENTIAL**5.2.4 Subject Withdrawals**

A subject may withdraw for any reason. The Investigator will advise the Sponsor of the withdrawal of any subject.

A subject may be withdrawn in any of the following circumstances:

- Adverse events;
- Protocol violation;
- Withdrawal of consent;
- Termination of the study by the Investigator or Sponsor.

Subjects who voluntarily withdraw are termed dropouts. Dropouts may be replaced following discussion with the Investigator and Sponsor. Subjects withdrawn due to an adverse event which is thought to be related to the study drug will not be replaced. This statement will not apply to Cohort 1 in the event that a subject is withdrawn prior to dosing in Treatment Periods 2 or 3. If a subject is withdrawn from Cohort 1, that subject may be replaced in order to allow a full cohort of 4 subjects to be dosed in the subsequent treatment period.

If a subject is withdrawn or withdraws during the inpatient stay the discharge procedures should be performed and follow-up assessments completed prior to them leaving. If a subject is withdrawn or withdraws after the inpatient stay is completed a follow-up visit should be scheduled.

If a subject is withdrawn due to an adverse event, appropriate medical care should be provided and the adverse event should be followed to resolution. Follow-up procedures should be conducted as scheduled.

CONFIDENTIAL

Synoptic Clinical Study Protocol
Version 2.0 - 05/08/2017

EudraCT Number: 2017-000380-33

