signs, ECGs, and clinical laboratory safety tests), and tolerability (adverse event profile) data up to and including 24 h postdose will be reviewed by Covance's clinical team prior to dosing the remaining subjects at that dose level. Dosing of the subsequent subjects in cohort 1 will be at the discretion of the Principal Investigator.

Treatments will be administered double blinded (except for Cohort 1, TP1 where it will be known that the 3rd and 4th subjects will receive the active dose); subjects will be blinded with regard to treatment and clinical staff will remain blinded with regard to treatment until the Safety Committee meeting.

An interval of at least 7 days will separate the dosing of the last subject in one cohort and dosing of the first subject in the next cohort to permit a timely review and evaluation of interim safety, tolerability and PK data. Safety, tolerability and PK data will be reviewed up to 48 hours post-dose prior to the dose escalation decision. If T_{max} is significantly later than predicted, PK data to a later timepoint may be reviewed prior to the dose escalation decision. The data of up to at least 3 subjects receiving Y14 in cohort 1 and 4 subjects, (i.e. a minimum of 3 subjects receiving Y14) in cohort 2 onwards will be reviewed before dose escalation.

Following a 28-day screening period eligible subjects will be admitted to the clinical unit on Day -1 (1 day prior to dosing) for eligibility checks and baseline assessments. On Day 1 subjects will receive a single dose of Y14 or placebo by SC injection, and will remain in the clinical unit under medical supervision until 72 h postdose (Day 4) or until C_{max} is achieved, whichever is the later.

Safety monitoring will include assessment of adverse events (AEs), physical examination, 12-lead ECGs, vital signs (blood pressure pulse rate and body temperature) and clinical laboratory safety tests (serum biochemistry, haematology, coagulation, thyroid stimulating hormone [TSH], FT4 and urinalysis).

Blood samples for biomarker (tryptase) will be collected immediately after any possible allergic or anaphylactic adverse reaction, and 12 hours later. These samples will only be analysed if relevant adverse reactions occur.

The PK evaluation will include measurement of plasma Y14 levels and associated PK parameters.

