Exploratory PD evaluation will include evaluation of visual analogue scales (VAS) of nausea and satiety. Subjects in Cohort 3 onwards will undergo food intake studies on Day -1 and Day 1. The timing of the food intake study may be modified according to emerging PK data.

Blood samples for immunogenicity assays will be collected prior to the first dose (Treatment Period 1) and at the final follow-up visit for the volunteers from Cohort 1 only (as these volunteers have received multiple doses of Y14).

All subjects will return for a follow up visit 14 days (\pm 1 day) after the final dose.

Following discharge of subjects and depending on emerging PK data, the subjects (except cohort 1, dose level 1 and 2) may return to the clinical unit for further outpatient visits. The

CONFIDENTIAL

Synoptic Clinical Study Protocol
Version 2.0 - 05/08/2017

EudraCT Number: 2017-000380-33

number of additional visits per subject will not exceed six and will not extend beyond 8 weeks after each final dosing occasion. If additional outpatient visits are scheduled the final outpatient visit will be considered to be the final follow up visit where the follow-up visit assessments will be performed.

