After each inpatient stay, subjects will return to the clinical unit for outpatient visits as described in Figure 5.1,

Safety monitoring will include assessment of adverse events (AEs), physical examination, 12-lead ECGs, vital signs (blood pressure, pulse rate and body temperature) and clinical laboratory safety tests (serum biochemistry, haematology, coagulation, TSH, FT4, and urinalysis).

Blood samples for biomarker (tryptase) will be collected immediately and 12 hours after any possible allergic or anaphylactic adverse reaction. These samples will only be analysed if there is a relevant adverse reaction.

The PK evaluation will include measurement of plasma Y14 levels and associated PK parameters.

Exploratory PD evaluation will include evaluation of the following: glucose tolerance (as assessed by a standard 75 g oral glucose tolerance test before and after treatment), energy intake at mealtimes, body weight, visual analogue scales (VAS) of nausea and satiety and enteropancreatic hormones.

Blood samples for immunogenicity assays will be collected predose and at the final follow-up visit.

Subjects will attend a final follow-up visit on Day 70-73. If deemed necessary, unblinding will be performed as outlined in Section 6.9.

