7.2.5 Immunogenicity

For assessment of immunogenicity, plain tube serum samples (6 mL blood volume) will be collected prior to the first dose and at the final follow-up visit for SAD Cohort 1 and the MAD study, as subjects will be receiving multiple doses of the same peptide in these studies. Samples will be analysed using a GLP compliant and validated assay method utilising an ELISA (bridging assay format) using rabbit positive control antibodies raised against Y14.

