7.3.2 Reporting of Adverse Events

All adverse events must be fully recorded in the adverse event book throughout the entire study period and will be transcribed into the subjects' CRF, whether or not they are considered to be drug-related. Signs and symptoms of each AE should be described in detail: onset time and date, offset time and date, description of event, severity, relationship to investigational product, action taken and outcome.

Adverse events should be followed until recovery to the normal state has been achieved. In the event of a subject not returning to the clinical unit, the outcome of this event will be recorded as lost at follow up.

Reporting of SAEs and SUSARs

SAEs occurring on this study will be reported to the Sponsor's medical representative [name] within agreed timelines. The Investigator will be requested to complete a separate SAE reporting form in addition to the information on the CRF and in the AE book.

The Medicines for Human Use (Clinical Trials) Regulations 2004 (Statutory Instrument 1031) and subsequent amendments define the following terms:

CONFIDENTIAL

Synoptic Clinical Study Protocol
Version 2.0 - 05/08/2017

EudraCT Number: 2017-000380-33

An adverse reaction is any untoward and unintended response in a subject to an investigational medicinal product which is related to any dose administered to that subject.

A suspected unexpected serious adverse reaction (SUSAR) which is fatal or life-threatening must be reported to the competent authority and ethics committee immediately (within 7 days) after the Sponsor became aware of the event. Any additional information must be reported within eight days of sending the first report.

A SUSAR which is not fatal or life-threatening must be reported to the competent authority and ethics committee as soon as possible (within 15 days) after the Sponsor becomes aware of the event.

If a clinical trial is being conducted at a trial site in a third country in addition to sites in the United Kingdom, the Sponsor of that trial shall ensure that all SUSARs occurring at that site are entered into the European database established in accordance with Article 11 of the EU Clinical Trials Directive.

As soon as practicable after the end of the reporting year, a Sponsor shall, in relation to each investigational medicinal product tested in clinical trials in the United Kingdom for which he is the Sponsor provide the licensing authority and the relevant ethics committees with -

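### A dosed subject who withdraws during an inpatient stay has follow-up done before leaving with no later visit called for, so for non-adverse-event leavers the last safety check can fall hours to days after a dose instead of weeks.

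*Combined protocol and SAP*

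**What the plan says.** Section 5.2.4 (Subject Withdrawals) sets the procedure by where the subject is when he leaves, not by time since dosing.

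- **During a stay:** where a subject "withdraws during the inpatient stay the discharge procedures should be performed and follow-up assessments completed prior to them leaving". No further visit is mentioned.
- **After a stay:** where a subject "withdraws after the inpatient stay is completed a follow-up visit should be scheduled". No interval from the last dose is given.
- **Because of an adverse event:** the next paragraph has the event followed to resolution and adds "Follow-up procedures should be conducted as scheduled".

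Planned follow-up is set elsewhere. For Part A, section 5.1.1 says "All subjects will return for a follow up visit 14 days" (±1 day) after the final dose. For Part B, section 5.1.2 says "Subjects will attend a final follow-up visit on Day 70-73".

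Section 7.2.5 says that immunogenicity samples "will be collected prior to the first dose and at the final follow-up visit for SAD Cohort 1 and the MAD study". Sections 9.2.4 and 10.5 report the result as yes or no and give no rule for a sample taken early. Section 10.3 keeps every dosed subject in the safety population.

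**The concern.** Doses are given in the unit, so withdrawal during a stay is usually withdrawal soon after a dose. The subjects closest to dosing get the shortest observation, while a subject who leaves after discharge gets a visit.

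Safety and tolerability is the primary objective of a first-in-human study. Section 3.2 describes the product as a sustained-release formulation. Section 5.1.1 allows the Part A stay to run past 72 h if Cmax has not been reached, and section 7.2.2 provides for a tmax beyond 24 h. A subject who leaves on the first day could therefore have his last check before peak exposure.

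Cohorts are small. Under sections 5.1.1 and 5.1.2 a dose level has 3, 5 or 6 subjects on Y14, so one shortened follow-up is 33%, 20% or 17% of that level's active subjects. All of them stay in the safety population, and nothing separates shortened from full follow-up.

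The antibody result has a similar weakness. It rests on a single post-dose sample tied to the final follow-up visit. If that sample moves forward with the other assessments, a very early result is summarised with the planned ones.

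**Working it through.** The plan gives no figure for this point, and section 10.2 says that the sample size was not statistically determined. The check is date arithmetic on the plan's own visit days.

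**Inputs**
- Part A stay: to 72 h after dose, or until Cmax if later (5.1.1, 5.2.3).
- Part A follow-up: 14 ± 1 days after the final dose (5.1.1).
- Part B doses: Days 1, 8, 15, 22 and 29 (5.1.2).
- Part B stays: Days -2 to 4, 8-9, 15-16, 22-23, 29-31 and 36-37 (5.2.3). Stays 2-4 last at least until 24 h after dose (5.1.2).
- Part B final follow-up: Day 70-73 (5.1.2).

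**Part A.** Planned interval: 14 - 1 = 13 to 14 + 1 = 15 days. Under the in-stay rule: 0-72 h, longer if Cmax is later.

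**Part B.** Latest in-stay check = discharge day minus dose day. Planned interval = (70 to 73) minus dose day. Time since first dose = (dose day to discharge day) minus 1; for stay 6 it runs from admission to discharge.

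| Stay | Last dose | In-stay check after last dose | Planned follow-up after that dose | Time since first dose on leaving |
|---|---|---|---|---|
| 1 | Day 1 | up to 4 - 1 = 3 days (72 h) | 69-72 days | 0-3 days |
| 2 | Day 8 | up to 9 - 8 = 1 day (about 24 h) | 62-65 days | 7-8 days |
| 3 | Day 15 | up to 16 - 15 = 1 day (about 24 h) | 55-58 days | 14-15 days |
| 4 | Day 22 | up to 23 - 22 = 1 day (about 24 h) | 48-51 days | 21-22 days |
| 5 | Day 29 | up to 31 - 29 = 2 days (48 h) | 41-44 days | 28-30 days |
| 6 | Day 29 | 36 - 29 = 7 to 37 - 29 = 8 days | 41-44 days | 35-36 days |

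Across the five doses the planned interval runs from 41 to 72 days.

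**Immunogenicity.** Table 7.2 lists 2 samples of 6.0 mL, 12.0 mL in total. One is taken before the first dose, which leaves one after dosing. Samples are planned for 4 subjects in Cohort 1 and 24 in Part B, so 28 of 28 + 24 = 52 planned subjects. That is the number whose single post-dose sample is tied to this visit, not a forecast of how many will leave early.

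**The two paragraphs of 5.2.4 side by side.** A subject withdrawn for an adverse event during a stay meets both conditions. One instruction completes follow-up before he leaves; the other keeps it on schedule. The section does not say which governs or whether both apply. Section 5.1.1 adds that all Part A subjects return, without an exception for withdrawals.

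**The case against.** The strongest reply is that the subjects of most interest are already protected. Adverse-event withdrawals have their own paragraph with follow-up on schedule. Section 3.2 makes severe and persistent nausea, or severe vomiting, thought to be due to the product a reason for withdrawal, so those cases fall under it. The paragraph can be read as adding to the in-stay rule. This largely stands: the clear gap is for leavers without an adverse-event withdrawal, and for the others the fault is an unreconciled instruction. It does not remove the point. Section 3.2 says that mild to moderate nausea is not a cause for withdrawal, so a subject who chooses to leave with it could be classed as a voluntary dropout.

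A reader might infer that early leavers give no safety data after discharge. The documents do not support that. Section 7.3.2 says "Adverse events should be followed until recovery to the normal state has been achieved", and section 5.2.3.3 collects partner pregnancies to 3 months after the final dose. What may be lost is new, late-onset information.

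A reader might also infer that the antibody sample is always too early or is disturbed by remaining drug. The documents give no time to antibody response, no statement on drug interference and no human half-life. Exposure also starts at the first dose: a Part B subject who leaves in stay 5 is already 28-30 days from it, and a Cohort 1 subject in the third treatment period is at least 14 days from the first period's dosing. The concern is confined to those who leave after an early dose.

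Finally, assessing a subject before he goes secures data that might otherwise be lost. That is a good reason to keep the leaving-day assessment, but not to make it the only one.

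**Conclusion.** The point holds for dosed subjects who leave during a stay for reasons other than an adverse event. Followed as written, section 5.2.4 can put the last safety check at about 0-72 h instead of 13-15 days in Part A. In Part B, stays 1-5, it can fall within about 1-3 days of a dose instead of 41-72 days. In stay 6 it falls 7-8 days after the last dose, so the problem is milder there. For adverse-event withdrawals during a stay, the finding is that two sentences conflict and must be reconciled.

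This rests on three assumptions. The planned weekly regimen and stays are used, although the plan allows both to change; Part A stays can also extend to Cmax, and added outpatient visits could move final follow-up later. The follow-up assessments are taken to include the immunogenicity sample; this is inferred from sections 5.1.1, 5.1.2 and 7.2.5, because the schedule of events is not in the text available. The number affected is unknown, as no dropout rate is given.

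**What to change.** Reword the in-stay sentence of section 5.2.4. Discharge procedures are done before leaving, and every dosed subject, whatever the reason for withdrawal, is also invited to the planned follow-up visit for his study part, unless he withdraws consent to further contact. In Cohort 1 and Part B the immunogenicity sample is taken at that visit.

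Keep the sentence that follow-up is conducted as scheduled, and make the two paragraphs consistent with it and with section 5.1.1.

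In sections 9.2.4 and 10.5, state that where a leaving-day antibody sample is the only post-dose sample, it is listed as early and kept apart from the final follow-up summary.

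The cost is a wording amendment and one already-planned visit for a few subjects. Some will decline to return, and for them the leaving-day assessment remains the last one.
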